Between January 2011 and November 2013, 48 patients in the Dent Dizziness and Balance Center were diagnosed with Ménière's disease and were prescribed lamotrigine as an off-label treatment. These patients were given a definitive or probable diagnosis based on the AAO-HNS 1995 criteria and had experienced at least three attacks in the three months prior to treatment. Almost all patients had been previously seen by ENT or other specialists and had tried conventional treatments like an improved life style, a low-sodium diet and diuretics. Some patients even attempted surgical treatments. Dosages varied from 50-300mg daily; most patients experienced a reduction of vertigo attacks during titration, but if another attack occurred the dose was increased further. We found that 13 of the 48 patients (27.1%) were also diagnosed with some form of anxiety, six individuals (12.5%) with only migraine and 21 individuals (43.8%) with an anxiety disorder and migraine. Out of these 48 individuals, ten were lost to follow-up and four patients had side effects like rash and had to discontinue the medication. After removing the above 14 patients, 94.1% (32/34) of remaining individuals reported improvement in symptoms, especially a reduction of Ménière's vertigo attacks. Furthermore, 50% (16/32) of improved patients experienced complete vertigo attack remission. Before initiation of lamotrigine therapy, 48 patients reported a mean of 13.5 (SD=12.5) vertigo attacks in the preceding three months (Figure 1). Thirty-five of the patients completed the initial follow-up and

reported a mean of 4.9 (SD=7.2) vertigo attacks in the three months after starting lamotrigine, *p<0.0001 (Wilcoxon signed rank test). Twenty-eight patients reported a mean of 2.5 (SD=5.5) vertigo attacks after completion of a three-month maintenance dose, *p<0.0001 (compared to before lamotrigine). Vertigo attack reduction and remission was not affected by migraine comorbidity.

2.3 Provide the scientific or scholarly background for, rationale for, and significance of the research based on the existing literature and how will it add to existing knowledge.

Response:

Please refer to 2.1

2.4 Include complete specific citations/references.

Response:

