Following the screening visit, participants will enter a four week lead-in period. They are responsible for recording vertigo and other symptom severity, and abortive medication use with the Ménière's daily survey. During this period any uncompleted audiogram or EKG testing can take place. This lead-in period will provide a more accurate representation of the Ménière's disease vertigo frequency and allow for screening tests to be completed at the participant's convenience. If the participant is on any prohibited medication at the screening, the medications will be discontinued if the participant wishes to continue in the study and it is deemed safe by the PI and the prescribing doctor. The lead-in period will also be used as a wash-out.

At Visit 2, after the four week lead-in, inclusion/exclusion criteria will be re-evaluated. This includes a review of any concomitant

medications. Participants will be asked to hand in their Ménière's survey if they opted for the paper document. The surveys will be reviewed to ensure that abortive measures were only used during the severe attacks, as instructed. The Principal Investigator will assess any possible adverse events and then staff will administer the questionnaire batch. If the participant is eligible for randomization, he/she will be assigned to either a placebo or lamotrigine treatment group. Assignment will be based on a randomization conducted by UBSoPPS Research pharmacists, and the participant will be considered "enrolled" in the study at this point, and from this point on, all medical services, except abortive medication(s) of the patient's choice) are study-related and are not billed to the patient's insurance.

- 3.3 Indicate specifically whether you will include or exclude each of the following special populations: (You may not include members of these populations as subjects in your research unless you indicate this in your inclusion criteria.)
 - *Adults unable to consent*
 - Individuals who are not yet adults (infants, children, teenagers)
 - Pregnant women
 - Prisoners

Response:

Exclude all

3.4 Indicate whether you will include non-English speaking individuals. Provide justification if you will exclude non-English speaking individuals.

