7.0 Study Timelines

7.1 Describe the duration of an individual subject's participation in the study.

Response:

The study is composed of five phases: medical history qualification (eight weeks), lead-in (four weeks), titration (six weeks), study period (12 weeks), and taper (two weeks).

7.2 Describe the duration anticipated to enroll all study subjects.

Response:

1-2 years

7.3 Describe the estimated date for the investigators to complete this study (complete primary analyses)

Response:

06/2016

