8.0 Study Endpoints

8.1 Describe the primary and secondary study endpoints.

Response:

The endpoints of this study are:

Primary Efficacy Endpoint:

• Comparison between lamotrigine and placebo groups of the reduction of Ménière's vertigo attacks from baseline

Secondary Efficacy Endpoints:

- Comparison between lamotrigine and placebo groups of vertigo attacks:
- Responder rate: Percentage of patients with > 50% reduction in vertigo attack frequency during treatment vs. baseline
- Vertigo attack free rate analysis: Length of vertigo attackfree intervals, number and percentage of vertigo attack-free days per 28 days period, number and percentage of patients who are vertigo attack-free during the double blind phase
- Comparison between lamotrigine and placebo groups of hearing loss:
- Analysis of audiograms between baseline and end of the study
- Comparison between lamotrigine and placebo groups of symptom severity:
- Ménière's Disease Patients-Oriented Severity Index (MDPOSI)
- Tinnitus Handicap Inventory (THI) questionnaire
- Clinical Global Impression-Severity & Change
- Comparison between lamotrigine and placebo groups of quality of life:
- Dizziness Handicap Inventory (DHI) questionnaire
- AAO-HNS Ménière's disease self-assessment

- Patient Health Questionnaire-9 (PHQ-9)
- Generalized Anxiety Disorder 7-item scale (GAD-7)

8.2 Describe any primary or secondary safety endpoints.

Response:

N/A – no such endpoints

9.0 **Procedures Involved**

9.1 Describe and explain the study design.

Response:

This is a randomized double-blind pilot proof-of-concept clinical trial. The principal investigator and all staff involved in clinic visits will remain blinded until the blind is scheduled to be broken or there is an emergency.

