Participants who are diagnosed with Ménière's disease, as determined by clinical history, ENT confirmation and an audiogram, will qualify if they also have had two or more Ménière's vertigo attacks in a four-week span for two consecutive four-week periods (the qualification period). Those who meet these criteria will then need two or more Ménière's vertigo attacks during a four-week lead-in period to further establish a baseline and verify randomization eligibility. Participants are allowed from the beginning of the lead-in to take their choice of a symptomatic abortive medication according to its package instructions for Ménière's vertigo attacks that last longer than 30 minutes with nausea and/or vomiting. Symptomatic abortive medications include, but are not limited to, meclizine (Antivert), Valium, diazepam, or Zofran. The abortive medication can be used throughout the study regardless of treatment assignment and its use will be recorded. Twelve eligible participants, with a minimum total of six attacks during the qualification and lead-in periods, will be randomly assigned to either a placebo or lamotrigine treatment group. Randomization will be conducted by UBSoPPS Research Pharmacy. The study drug and matching placebo will be titrated from 25mg twice a day (BID) up to 150mg BID over a six week period. During titration, clinic visits are scheduled every two weeks to assess any adverse events, symptoms, quality of life, and compliance. Those who cannot tolerate the 150mg BID dose may return to a 100mg BID dose during an unplanned visit. However, if a participant is unable to tolerate the 100mg BID dose they will be withdrawn from the study. Participants will maintain the 150mg BID or 100mg BID dose for a 12-week period with clinic visits every four weeks to assess their progress. Between all study visits, participants are asked to complete a daily survey describing their symptoms. This survey is hosted by polleverywhere.com and can be completed through text message, an online website, or with a paper document- whatever method is preferred by the participant. At the conclusion of the 12-week study period, a study staff will be un-blinded

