11.0 Data Management

11.1 Describe the data analysis plan, including any statistical procedures.

Response: The primary response will be the number of vertigo attacks as measured at baseline and at the end of the study period. The secondary responses will include the percentage of vertigo free patients, audiograms, symptom severity scales and quality of life scales (listed in the Approach section). The analysis set will include all subjects who are randomized and receive at least one dose of the study medication or the placebo. Integer or continuous variables will be presented by their mean and median and their SD and IQR. Categorical variables will be summarized using counts and percentages. Demographic and baseline characteristics of the enrolled subjects will be summarized through descriptive statistics for continuous variables and through frequencies for categorical variables. Demographic and baseline characteristics of the intervention and placebo groups will be compared to assess for comparability. Continuous variables will be compared using Wilcoxon rank-sum test and categorical variables will be compared through Fisher's exact test. We will test for reduction in the Ménière's vertigo attacks from baseline through Wilcoxon's sign rank test and will compare the reduction between the two treatment groups using Wilcoxon rank-sum test. The tests will be two-tailed and the significance level will be set to 0.05. Additionally, we will perform statistical modeling of the number of vertigo attacks longitudinally through generalized linear mixed effects model using Poisson or Negative Binomial distribution as appropriate. Data analysis will be conducted using SAS (SAS Institute Inc., Cary, NC, USA) and R (http://www.r-project.org/). All data analyses will be performed by [name] of the SUNY UB Statistical Consultant Laboratory.

11.2 Provide a power analysis.

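### The primary rank-sum test on an unadjusted reduction in attacks, most naturally an absolute change, usually gives up power that a baseline-adjusted analysis of the same counts would keep; the scale and windows also need fixing

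*Combined protocol and SAP*

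**What the plan says.** Section 8.1 gives the primary endpoint as "Comparison between lamotrigine and placebo groups of the reduction of" attacks from baseline. Section 11.1 adds "The primary response will be the number of vertigo attacks as measured at baseline and at the end of the study period", tests the within-group reduction with a signed-rank test, and "will compare the reduction between the two treatment groups using Wilcoxon rank-sum test", two-sided at 0.05. A longitudinal Poisson or negative binomial mixed model is additional, and no baseline term is named for it.

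Three things are not fixed.

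- **Scale.** A percent scale appears only in the secondary responder rate, a "reduction in vertigo attack frequency during treatment vs. baseline".
- **Baseline window.** Section 9.1 requires two or more attacks "during a four-week lead-in period to further establish a baseline and verify randomization eligibility", but also sets a minimum of six attacks over qualification and lead-in together, which is 8 + 4 = 12 weeks. Section 7.1 describes the eight qualification weeks as medical history. The daily survey starts at the lead-in, and Section 3.2 says "This lead-in period will provide a more accurate representation of the" attack frequency.
- **Follow-up window.** The end of the study period could mean all 12 weeks or the last four. The responder wording could also take in titration.

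Section 11.1 analyses everyone randomised and dosed. Section 13.3 ends data collection at withdrawal. No rule connects the two.

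**The concern.** A change score subtracts the whole baseline count, however weakly that count predicts follow-up. Attack counts vary a good deal within a patient, so part of what is subtracted is noise, and a four-week or recalled baseline is noisier still. A regression on baseline estimates the weight instead of fixing it at one, using data already collected. With 12 patients, later 16, the lost power matters.

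The unstated scale and windows are a second issue. Under Section 9.2 a staff member opens a treatment code at each participant's Visit 8, and under Section 12.1 incoming data are analysed and reviewed every two weeks. Details left open could therefore be settled after outcomes have been seen.

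**Working it through.** **Inputs from the documents.** 6 per arm (N = 12, Section 9.1) or 8 per arm (N = 16, Section 11.2 update); two-sided 0.05; means of 5 v 13 and SD 7.24 (Section 11.2); entry rule of at least two attacks in each of three four-week windows (Section 3). For remission, Section 2.2 reports "50% (16/32) of improved patients experienced complete vertigo attack remission". That is 16/34 = 47% of those followed or 16/48 = 33% of all treated.

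**Assumed, not in the documents.** The baseline to follow-up correlation, the spread of patient rates, and within-patient overdispersion.

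**1. The plan's own power.** Simulating a two-group negative binomial regression (Wald test, same SD in both arms, 6000 iterations) for N = 12 gives:

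- 5 v 13, SD 4: 88.8 (stated 86.6)
- 6 v 13, SD 4: 84.0 (stated 83.5)
- 5 v 13, SD 7.24: 55.3 (stated 57.6)

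Of the 16 rows, 11 agree within 2 points and all within 4. The table therefore reproduces, but it describes a regression on end-of-study counts, not the rank-sum test on reduction.

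**2. Why absolute change loses.** For baseline B and follow-up Y with correlation ρ, Var(Y − B) = σY² + σB² − 2ρσYσB. After linear adjustment the variance is σY²(1 − ρ²). The difference is (σB − ρσY)², which is never negative. With equal SDs the ratio of adjusted to change variance is (1 + ρ)/2. At ρ = 0.53 that is 0.765. This is only a guide, since the counts are skewed and the test uses ranks.

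**3. Simulation A: 6 per arm, 30 scenarios.** Gamma patient rates (shape 1.28, 4 or 10); overdispersion none or gamma shape 2 per four weeks. Five effects: ratio 5/13; the same ratio with log-normal variation (SD 0.7); 47% remission; 33% remission; 13 − 5 = 8 attacks subtracted. That is 3 × 2 × 5 = 30. The untreated mean is 13 after the entry rule, and the log correlation runs from 0.15 to 0.68. All C(12,6) = 924 labellings are enumerated, with 1500 or 2000 replicates. The adjusted analysis is log(follow-up + 0.5) on log(baseline + 0.5) and arm.

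| Baseline | Gain over absolute | Gain over percent |
|---|---|---|
| 12 weeks | +2 to +26 points | −5 to +8 |
| Lead-in | +13 to +41 | +1 to +17 |

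- Largest 12-week gain: 59% v 33%, with overdispersion. Largest lead-in gain: 87% v 46%.
- Smallest gains come with remission and no overdispersion: 57% v 52%, 57% v 53% and 58% v 52% (47% remission); 62% v 60%, 64% v 62% and 65% v 62% (33% remission). With a placebo mean of 20 it is 59% v 58%.
- Percent instead of absolute, on 12-week windows, is by itself worth 4 to 23 points.
- At 8 per arm (12 scenarios, 12-week baseline): +5 to +34 over absolute, −4 to +12 over percent.
- Under the null the adjusted test rejected 3.9% to 5.2%.
- Offset: 0.05 in place of 0.5 cost up to 9 points; 1.0 moved power by −0.5 to +2.8.

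**4. Simulation B: a separate paired-count model, N = 12, 36 proportional-effect scenarios.** Loss in points against the log model with a 12-week baseline:

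| Rank-sum on | Median (range) |
|---|---|
| Absolute, 12 v 12 weeks | 19 (9 to 27) |
| Absolute, lead-in × 3 v 12 weeks | 29 (17 to 43) |
| Percent, 12 v 12 weeks | 2.7 (−2 to 5) |
| Percent, lead-in v 12 weeks | 8 (4 to 18) |

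In 36 further scenarios where the drug subtracts attacks, the 12 v 12 losses were 25 (3 to 37) for absolute and 7 (−6 to 10) for percent. One worked case (placebo SD 8.3, lamotrigine SD 6.7, assumed correlation 0.53, 12 v 12 weeks) gave absolute 39%, percent 55%, log model 57% and rank ANCOVA 50%.

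**The case against.** The strongest reply is that the documents say more than a literal reading suggests. Section 11.1 defines the response as a number of attacks and applies a signed-rank test to the same reduction, which normally means paired differences. The means in Section 11.2 come from the three-month counts of Section 2.2, and entry pools 12 weeks. Percent and the during-treatment wording belong to a secondary endpoint. This stands: absolute change over 12 v 12 weeks is the best-supported reading, and the larger lead-in figures apply to readings with less support. A reader might infer that the primary endpoint is wholly undefined, or the test invalid. The documents support neither.

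Second, the gain is not from adjustment as such. For percent reduction with a lead-in baseline, only 39% of proportional and 3% of subtraction scenarios in simulation B lost more than 2 points against rank ANCOVA. In the worked case that unadjusted test beat rank ANCOVA, 52% v 49%. This also stands.

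Third, the planned mixed model could recover the power. It could if it were primary and used baseline, but the plan states neither.

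Fourth, the simulations fix a 6:6 split and have no withdrawals. Section 9.4 can be read as simple randomisation, under which 6:6 has probability 924/4096 = 23%, although Section 11.2 aims at equal groups. Two dropouts are reported. These limits stand.

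A reader might also infer that these choices move power by more than most design changes could. That is not shown. Sample size is the only comparator available, and going from 6 to 8 per arm raised adjusted power from 51% to 68%. Those 17 points lie inside the 4 to 23 from choosing percent over absolute.

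**Conclusion.** The point holds as an avoidable loss of efficiency joined to an incomplete definition. On the best-supported reading, the primary test usually loses roughly 2 to 27 points of power at 6 per arm against a log-count analysis adjusted for baseline. One set with a subtractive effect reached 37, and some remission scenarios showed almost no loss. A lead-in baseline makes the loss larger. Percent reduction on matched 12-week windows loses little or nothing under proportional effects and up to about 10 points under subtractive ones. With a lead-in baseline it loses a modest amount against the log model and often none against rank ANCOVA.

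All sizes rest on an assumed correlation and assumed heterogeneity, so the direction is firmer than the amounts. Nor does adjustment rescue the sample size: with a treated-arm SD of 7.1, close to the pilot's 7.24, adjusted power was 51% at 6 per arm and 68% at 8.

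**What to change.** Issue a dated amendment, locked by people without treatment codes and stating what data had been seen.

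1. State the scale and the baseline and follow-up windows. Note that qualification counts come from history and lead-in counts from the daily survey.
2. Compare arms with a baseline-adjusted analysis, for example log(12-week count + 0.5) on log(baseline count + 0.5) and arm. Fix the offset in advance, and take the p-value by permutation under the allocation actually used. Report a ratio of (attacks + 0.5), and keep the rank-sum on reduction as a sensitivity analysis. If the sponsor will not change the primary test mid-trial, keep the rank-sum but on percent reduction over matched 12-week windows, with the adjusted analysis as supporting.
3. Include log baseline in the planned mixed model.
4. State how withdrawals enter, for example by a count model with log diary days as offset or a minimum number of diary days, plus a completers-only repeat. Do not add 0.5 to very short diaries: an attack-free patient with 7 days would score (0.5/7) × 84 = 6 attacks per 84 days, against 0.5 for an attack-free completer.

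The cost is about half a page and short code, with no new data. Changing the primary test after 8 completions, with codes opened at Visit 8, carries a credibility cost. The percent-reduction route costs less and, with a 12-week baseline, secures most of the gain. The adjusted effect reads as a ratio rather than attacks avoided.

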Response: According to our preliminary data, the mean number of vertigo attacks after 3 months of treatment with Lamotrigine was 4.91 (SD=7.24), and we expect the mean number of vertigo attacks in the placebo group to be approximately 13. We assumed Negative Binomial distribution for the response, two-sided tests, level of significance 0.05 and considered various sample sizes, mean and variance of the number of attacks in the two groups. We calculated the associated power for comparison of the mean response between the two groups by utilizing Monte Carlo simulations and using Negative Binomial regression model with log link. Each simulation consisted of 1000 iterations and was conducted in R (http://www.r-project.org/). This analysis showed that a power above 80% can be obtained with a sample of 12 participants.

Table: Associated Power for Comparison of the Mean Response between Treatment Groups Calculated with Monte Carlo Simulations and Negative Binomial Regression Model with Log Link

Total N	Mean Number	Standard	Mean Number	α	Power
	of Attacks in	Deviation of	of Attacks in	level	
	Lamotrigine	the number of	Placebo group		
	group at the end	attacks	at the end of		
	of the study		the study		
12	5	7.24	13	0.05	57.6
12	5	6	13	0.05	60.6
12	5	4	13	0.05	86.6
12	6	6	13	0.05	58.2
12	6	4	13	0.05	83.5
14	5	7.24	13	0.05	60.7
14	5	6	13	0.05	70.1
14	5	4	13	0.05	92.8
20	5	7.24	13	0.05	67.6
20	5	4	13	0.05	97.6
20	5	7.24	12	0.05	60.4
20	5	4	12	0.05	94.5
20	6	7.24	12	0.05	48.8
20	6	4	12	0.05	91.9
34	5	7.24	13	0.05	82.2
34	5	6	13	0.05	92.5

Update on 6/4/2015:

As of 6/4/2015		
Expected N complete		
Complete		
Currently enrolled		
Potentially eligible, not enrolled		
Screened & eligible but declined participation in study		
Screened and ineligible		
Started study but dropped out		
TOTAL		

We engage in a multi-step process to reduce drop-outs, however, this is a very long study (6 months), and some drop-outs are to be expected. Thus far, we've had 2 participants drop out of the study and 8 have completed. Therefore, our dropout rate is 25%. To compensate for drop-outs, we request to increase our enrollment by 25%, rounded to the nearest whole number attain equal numbers in each group, for a total N of 16.

11.3 Describe the steps that will be taken secure the data (e.g., training, authorization of access, password protection, encryption, physical controls, certificates of confidentiality, and separation of identifiers and data) during storage, use, and transmission.

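### The power table in 11.2 is labelled two-sided alpha 0.05, but the negative binomial test that reproduces most of it rejects a true null about 8 to 12% of the time at 6 to 8 per arm, so part of the stated power is excess type I error

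*Combined protocol and SAP*

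**What the plan says.** Section 11.2 takes a lamotrigine mean of 4.91 (SD 7.24) from the preliminary data and states that "we expect the mean number of vertigo attacks in the placebo group to be approximately 13". Power is simulated for a comparison of the two means "using Negative Binomial regression model with log link", under "two-sided tests, level of significance 0.05". "Each simulation consisted of 1000 iterations". Every row of the table carries 0.05 in its alpha column. The text concludes that 12 participants suffice for power above 80%. The June 2015 update raises enrolment to 16 in equal groups, to allow for drop-outs.

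Section 11.1 names a different test for the primary comparison: the plan "will compare the reduction between the two treatment groups using Wilcoxon rank-sum test". It then says: "The tests will be two-tailed and the significance level will be set to 0.05". After that it adds longitudinal modelling of the counts by a "generalized linear mixed effects model using Poisson or Negative Binomial distribution as appropriate".

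Neither section names the test statistic for the count models (Wald, likelihood ratio or other), a small-sample reference distribution, a check of rejection under the null, or a rule for choosing between Poisson and negative binomial.

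**The concern.** Wald tests from negative binomial regression rely on large samples. With 6 to 8 patients per arm the dispersion is estimated from 12 to 16 counts and then treated as known, so the standard error tends to be too small. A simulated power from such a test mixes real sensitivity with a false-positive rate above 5%, and the alpha column then describes a test that the design does not have.

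The sample-size justification is at stake. Only two of the five N=12 rows exceed 80%, both at SD 4, so a few points decide whether the conclusion stands. A lesser risk is that the additional mixed model, read without a small-sample correction, is taken as support when the rank-sum test is not significant.

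**Working it through.** **Inputs, all from 11.2.** Lamotrigine mean 5 or 6, placebo mean 13, SD 4, 6 or 7.24, two-sided 0.05, and 6 per arm (N=12) or 8 per arm (N=16). Assumption: the tabulated SD applies to both arms. A common dispersion parameter instead gives only 63 to 65% for the two SD 4 rows, so it does not reproduce the table.

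**Model.** Counts are negative binomial with dispersion θ = μ²/(SD² − μ):
- mean 5, SD 7.24: 25/(52.42 − 5) = 0.53
- mean 5, SD 4: 25/(16 − 5) = 2.27
- mean 6, SD 4: 36/(16 − 6) = 3.6
- mean 13, SD 7.24: 169/(52.42 − 13) = 4.29
- mean 13, SD 4: 169/(16 − 13) = 56.3, close to Poisson

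**Test.** Maximum-likelihood fit with a common θ, then z = (log ȳ_P − log ȳ_L) / √[(1/n)(1/ȳ_L + 1/θ̂) + (1/n)(1/ȳ_P + 1/θ̂)], compared with 1.96.

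**Step 1: reproduce the plan's figures.** With 1000 iterations the plan's own simulation error is √(0.835 × 0.165/1000) = 1.2 points at 83.5% and √(0.576 × 0.424/1000) = 1.6 points at 57.6%.

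| N=12 row | Stated | Wald z, repeated simulations |
|---|---|---|
| 6 vs 13, SD 4 | 83.5 | 83.0 to 83.9 |
| 5 vs 13, SD 4 | 86.6 | 89.0 to 90.3 (likelihood ratio 87.1) |
| 5 vs 13, SD 7.24 | 57.6 | 54.8 to 57.7 |
| 6 vs 13, SD 6 | 58.2 | 55.9 to 58.2 |
| 5 vs 13, SD 6 | 60.6 | 63.5 to 65.6 |

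In one run over all 16 rows, 9 fell within 2 points and the rest within 5. The Wald z form is therefore a good, though not exact, account of the table.

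**Step 2: same code, equal means.** Rejection in per cent at nominal 5% (1500 runs per cell, standard error about 0.8 points at 10%):

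| Common mean, SD | Wald, 7 per arm | Wald, 8 per arm | Likelihood ratio, 8 per arm | Rank-sum, 8 per arm |
|---|---|---|---|---|
| 5, 7.24 | 10.5 | 10.8 | 8.1 | 3.7 |
| 5, 6 | 9.8 | 8.2 | 6.7 | 3.9 |
| 5, 4 | 9.3 | 10.3 | 8.2 | 5.3 |
| 6, 4 | 8.5 | 8.1 | 6.7 | 3.8 |
| 13, 7.24 | 10.5 | 8.6 | 7.3 | 3.9 |
| 13, 6 | 8.0 | 8.8 | 7.3 | 3.9 |
| 13, 4 | 6.6 | 5.9 | 5.1 | 4.1 |

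At 6 per arm, separate simulations gave 9.2 to 11.3%, 9.4 to 12.1% and 9.9 to 12.0% for most inputs, and 5.4 to 7.0% at mean 13, SD 4. Standard R software (800 runs per cell) gave 7.8, 9.6 and 14.0% in three cells and 5.4% at mean 13, SD 4. Across 6 to 8 per arm the likelihood-ratio test gave 5.1 to 9.0%, a t reference with N − 2 degrees of freedom 3.7 to 8.1%, and the rank-sum test 3.0 to 5.3%.

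**Step 3: power at N=12 with a test that holds 5%.** This was done either by permuting arm labels (all 924 splits at 6 per arm) or by recalibrating the Wald critical value under the null.

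| Row | Stated | Test holding 5% | Rank-sum on end counts |
|---|---|---|---|
| 6 vs 13, SD 4 | 83.5 | 73 to 81 | 68 to 70 |
| 5 vs 13, SD 4 | 86.6 | 82 to 88 | 79 to 81 |
| 5 vs 13, SD 7.24 | 57.6 | 47 to 52 | about 53 |

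The lower end of the two SD 4 ranges comes from permutation or from calibrating at the lower mean. The upper end comes from calibrating at mean 13. In the last row, recalibrating the Wald test gave slightly less, 44.5 to 47.7%.

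**The case against.** **The plan never says Wald.** This is true, and the inflation depends on the statistic: the likelihood-ratio test gives 5.1 to 9.0% and a t reference 3.7 to 8.1%. But Wald z reproduces most rows, and the likelihood-ratio test is also above 5% for most inputs. What stands is that the size of the excess is inferred from the reproduction and is not read from the text.

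**At mean 13, SD 4, the test is near nominal.** This also stands, and it matters because those are the placebo inputs of the two rows above 80%. Calibrated there, 6 versus 13 gives about 81% and 5 versus 13 about 87 to 88%. Calibrated at the lower mean, they give about 73 to 77% and 82 to 83%. A reader might infer that the 80% claim is simply false. The documents do not support that: the 5 versus 13, SD 4 row stays above 80% with either calibration.

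**The primary inference is elsewhere.** A reader might infer that the trial's primary alpha is inflated. It is not: the primary comparison is the rank-sum test, which rejects 3 to 5% under the null. The 0.05 sentence in 11.1 follows the Wilcoxon tests, and the mixed model is introduced afterwards as an addition in a pilot trial.

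**The Poisson option.** The pilot variance is about ten times the mean (7.24²/4.91 = 10.7), so a reader might expect false-positive rates of 27 to 57% if Poisson is chosen. Those rates belong to a Poisson regression without random effects. The plan specifies a mixed model, whose random intercept absorbs overdispersion between patients. At 6 per arm the Poisson mixed model gave 7 to 11% for the group effect and the negative binomial mixed model 6 to 11%. Higher rates appeared only with assumed within-patient variation: about 27% for Poisson group-by-time if half the overdispersion lies within patients, and 27 to 60% across both distributions if individual log rates drift with SD 0.5 to 0.8. The documents give neither quantity.

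**One test or two.** A reader might also treat the power-table regression and the longitudinal model as the same test. They differ: the first uses one end-of-study count per patient and no random effect. Type I error found for one does not carry over to the other.

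**Conclusion.** The point holds for the power table. At 6 to 8 per arm the test that best accounts for it has a true level of about 8 to 12% for most tabulated inputs, not 5%. Of the two N=12 rows above 80%, 6 versus 13 probably falls below that mark, and 5 versus 13 stays above it. Both use SD 4, well under the pilot SD of 7.24, at which power is about half. With the planned rank-sum test on end counts, the two rows give about 68 to 70% and 79 to 81%, so the 80% claim is at best borderline for the test that will be used.

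This rests on the Wald z form, the tabulated SD in both arms, equal allocation, and negative binomial counts as 11.2 assumes. The rank-sum power uses end-of-study counts, whereas the plan tests the reduction from baseline. The documents give no baseline-to-end correlation, so that power cannot be computed from them.

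For the longitudinal model the defect is smaller: an unstated reference distribution and an open choice of distribution. The mixed-model simulations are small (standard error about 2 points).

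**What to change.** In 11.2, recompute the table with a test that holds 5%, either the planned rank-sum test or a permutation test. Alternatively, keep the negative binomial test, name its statistic, and print the simulated type I error beside each power. Restate the sentence about 12 participants to match, naming the mean and SD on which it depends.

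In 11.1, make negative binomial with a random intercept the default for the additional model. Take the treatment p-value and interval from re-randomisation of the arm labels or another small-sample reference, such as a t or F distribution or a parametric bootstrap. State that this model does not replace the rank-sum result.

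The cost is a few sentences and a few lines of code. The stated power becomes somewhat less favourable. No change to trial conduct is needed.
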